4.2 Participant and Study Completion

An estimated subjects will be screened to enroll and randomize at least 316 subjects at approximately 10 sites with 158 subjects per each of the two treatment arms.

The study is planned to start with first patient first visit in October 2017 and is estimated be completed with last subject last visit occurring in June 2018.

4.3 End of Study Definition

The end of the study for an individual patient is defined as that patient's last clinic visit.

The end of the study for the overall trial is defined as the finalization of the Clinical Study Report.

4.4 Justification of Study Design

Based on CYS-002 results Novaliq plans a confirmatory study in DED patients having

(NEI grading) at baseline. This population responded best in signs and

symptoms.

The study will be a randomized, double-masked, vehicle controlled study to demonstrate efficacy and safety of CyclASol after 1-month treatment duration. Vehicle controlled studies are currently the standard for DED studies. Randomization and double masking are state of the art measures to reduce bias. Fast onset of efficacy is important for patients and their compliance to therapies, thus early demonstration of efficacy (e.g. at 1 month) is desired and highly clinically relevant. Moreover, DED is a fluctuating condition with phase-like recurring dry eye complaints that may be linked to seasonal and / or environmental changes (van Setten, *et al.* 2016), thus a primary endpoint assessment at a shorter treatment duration is considered clinically relevant and has a greater potential to capture the true drug effect.

Total corneal fluorescein staining (NEI grading) and total OSDI have been selected as the primary sign endpoint and primary symptom endpoint, respectively. The two primary endpoints will be tested in a sequential order with total corneal fluorescein staining being tested first. Both primary endpoints are well accepted by regulators and clinicians. The hierarchical testing has been selected to protect the α – error. Corneal staining is being tested first as the CYS-002 data for this endpoint is stronger.

4.5 Justification for Dose

The dose for this trial has been selected based on the previous CYS-002 study, which investigated two concentrations of CyclASol (0.05% and 0.1%). Neither the statistical analysis on the total population nor the modelling & simulation analysis identified a clear dose-response for sign or symptoms between the two CyclASol groups. However, there were some trends favoring CyclASol 0.1% over CyclASol 0.05% in symptoms in all subjects and in the target population for the current study (patients having total corneal staining of ≥ 10 at baseline). Moreover, the CsA amount applied with the CyclASol 0.1% is still lower than that of Restasis

Novaliq intends to pursue the concentration of CyclASol 0.1% for the current pivotal study CYS-003.

5 STUDY POPULATION

5.1 Number of Subjects (approximate)

An estimated subjects will be screened to enroll and randomize at least 316 subjects at approximately 10 sites with 158 subjects per each of the two treatment arms. Subjects meeting all of the inclusion criteria and none of the exclusion criteria will be enrolled into the study and randomized in a 1:1 ratio of CyclASol to vehicle.

5.2 Study Population Characteristics

All subjects must be at least 18 years of age, of either sex, and of any race. Furthermore, subjects must have a subject-reported history of dry eye in both eyes and meet all inclusion criteria and none of the exclusion criteria.

5.3 Inclusion Criteria

Each subject must:

- a. Be at least 18 years of age;
- b. Provide written informed consent;
- c. Have a subject reported history of Dry Eye Disease
- d. Be currently using (within 30 days before Visit 0) over-the-counter (OTC) eye drops, lubricating gels and/or artificial tears for dry eye symptoms at Visit 0;
- e. Have an OSDI score of at Visit 0 and Visit 1;
- f. Have a total corneal fluorescein staining score of
- g. Have a total lissamine green conjunctival score (sum of temporal and nasal regions) of
- h. Have an unanesthetized Schirmer's Test score
- j. Be able and willing to follow instructions and participate in all study assessments and visits.

5.4 Exclusion Criteria

[figure not shown]
Each subject must not:

a. Have any clinically significant slit-lamp findings at Visit 0 that require prescriptive medical treatment and/or in the opinion of the investigator may interfere with study parameters including trauma, Steven Johnson Syndrome, advanced epithelial basement membrane disease;

c. Have abnormal lid anatomy (e.g. incomplete eyelid closure, entropion, or ectropion) or abnormal blinking;

- g. Have a history of herpetic keratitis;
- h. Have active ocular allergies or ocular allergies that may become active during the study period;
- i. Be diagnosed with an ongoing ocular or systemic infection (bacterial, viral, or fungal), including a fever, or be undergoing treatment with antibiotics at Visit 0 or Visit 1;
- j. Have worn contact lenses within 90 days before Visit 0 or anticipate using contact lenses during the study;
- 1. Have used topical CsA or Lifitegrast within 60 days before Visit 0;
- n. Have had intraocular surgery or ocular laser surgery within 180 days before Visit 0, or have any planned ocular or eyelid surgeries during the study period;
- o. Be a woman who is pregnant, nursing, or planning a pregnancy;
- p. Be unwilling to submit a urine pregnancy test at Visit 0 and Visit 5 (or early termination visit) if of childbearing potential. Non-childbearing potential is defined as a woman who is permanently sterilized (i.e. has had a hysterectomy, bilateral tubal ligation, or bilateral oophorectomy), or is post-menopausal (i.e. without menses for 12 consecutive months);

q. Be a woman of childbearing potential who is not using an acceptable means of contraception. Acceptable methods of contraception include hormonal contraceptives (i.e. oral, implantable, injectable, or transdermal contraceptives), mechanical contraceptives (i.e. spermicide in conjunction with a barrier such as a diaphragm or a condom), intrauterine devices (IUD), or the surgical sterilization of the partner. For non-sexually active females, abstinence may be regarded as an adequate method of birth control; however, if the subject becomes sexually active during the study, she must agree to use adequate birth control as defined above for the remainder of the study;

r. Have an uncontrolled systemic disease;

aa. Have a condition or be in a situation (e.g. language barrier) which the investigator feels may put the subject at significant risk, may confound the study results, or may interfere with the subject's participation in the study significantly; or

5.5 Withdrawal Criteria (if applicable)

If at any time during the study the investigator determines that a subject's safety has been compromised, the subject may be withdrawn from the study in particular:

- the occurrence of an exclusion criterion which is clinically relevant and affects the subject's safety, if discontinuation is considered necessary by the investigator and/or sponsor.
- the occurrence of an AE if discontinuation of trial drug is desired or considered necessary by the investigator and/or the subject.
- the occurrence of pregnancy.

Subjects may withdraw consent from the study at any time without reason.

The sponsor and/or the investigator may discontinue any subject for non-compliance or any valid medical reason (see Section 8.6).

6 STUDY PARAMETERS

[figure not shown]
6.1 Efficacy Measures

6.1.1 Primary Efficacy Variable(s)

Two primary endpoints will be tested in the following order using hierarchical fixed sequence testing:

- 1. Change from baseline in total corneal fluorescein staining (NEI scale) at Day 29
- Change from baseline in Ocular Surface Disease Index (OSDI) at Day 29

6.1.4 Criteria for Effectiveness

Hierarchical fixed sequence testing will be employed to maintain the type I error rate. The primary analyses will first test the difference in the mean change from baseline corneal fluorescein staining (NEI scale) total score between treatments at Day 29. If the test of the difference is statistically significant at the two-sided alpha = 0.05 level in favor of CyclASol, then the study will be considered a success; CyclASol will be declared to be superior to vehicle in the mean change from baseline corneal fluorescein staining (NEI scale) total score at Day 29; and the difference in the mean change from baseline total OSDI score between treatments at Day 29 will be tested at the two-sided alpha = 0.05 level.

If in addition to a statistically significant test of the difference in the mean change from baseline corneal fluorescein staining (NEI scale) total score at Day 29 in favor of CyclASol, the test of the difference in the mean change from baseline total OSDI score at Day 29 is also statistically significant in favor of CyclASol, then CyclASol will be declared to be superior to vehicle in both the mean change from baseline corneal fluorescein staining (NEI scale) total score and the mean change from baseline total OSDI score at Day 29.

6.2 Safety Measures

These evaluations will be performed in an effort to ensure subject safety throughout the trial:

- Change in visual acuity from baseline at Visit 1 to Visits 2, 3, 4, and 5;
- Change in slit-lamp biomicroscopy findings from Visit 1 to Visits 2, 3, 4, and 5;
- Change in intraocular pressure from Visit 0 to Visit 3 and 5;
- Change in dilated fundoscopy findings from Visit 0 to Visit 5.
- Systemic and ocular AEs

7 STUDY MATERIALS

7.1 Study Treatment(s)

7.1.1 Study Treatment(s)/ Formulation(s)/ Medical Device Composition or Design

Run-In

• Systane Balance Lubricant Eye Drops

Randomized Study Treatments

- CyclASol 0.1% Ophthalmic Solution
- Vehicle Ophthalmic Solution (F4H5)

- 7.1.2 Description of for the Route of Administration, Dosage, Dosage Regimen, and Treatment Period(s).
 - At the end of Visit 0, qualified subjects will receive the run-in medication (Systane Balance). Their first dose of run-in will be in-office. They will then be instructed to dose at home BID up to and including the morning of Visit 1. Subjects will be instructed to dose in the morning and in the evening at bedtime. Subjects will record in the subject's diary that their doses were taken.
 - Study drug will be provided to sites as subject kits containing 3 bottles of CyclASol 0.1% Ophthalmic Solution or Vehicle Ophthalmic Solution.
 - At Visit 1, used/unused run-in will be collected from subjects. At the end of Visit 1, qualified subjects will be randomized and the first dose of study drug will be administered in the study center. The subject will receive the first bottle out of the assigned subject kit for dosing BID. Subjects will record in their diary that their doses were taken. A bottle should not be used after 30 days after opening; based on the use of visit windows for a subject this may be prolonged at the discretion of the Investigator.
 - At Visit 2, used/unused study drug will be collected from subjects for drug accountability. If the bottle is still intact and contains sufficient liquid it will be returned to the subject with instructions to continue to dose BID. If the bottle is not intact or there is insufficient liquid in the bottle, the subject will be dispensed a new bottle to continue BID dosing. Subjects will record in their diary that their doses were taken. A bottle should not be used after 30 days after opening; based on the use of visit windows for a subject this may be prolonged at the discretion of the Investigator.
 - At Visit 3 used/unused study drug will be collected from subjects for drug accountability. Subjects will receive their bottle from the same subject kit with instructions to continue to dose BID. The site must ensure that the study drug supply given to the subject is taken from the correct kit that was previously assigned to that subject. Subjects will record in their diary that their doses were taken. A bottle should not be used after 30 days after opening; based on the use of visit windows for a subject this may be prolonged at the discretion of the Investigator.
 - At Visit 4 used/unused study drug will be collected from subjects for drug accountability. Subjects will be dispensed the third bottle from the same subject kit with instructions to continue to dose BID. The site must ensure that the study drug supply given to the subject is taken from the correct kit that was previously assigned to that subject. Subjects will record in their diary that their doses were taken. A bottle should not be used after 30 days after opening; based on the use of visit windows for a subject this may be prolonged at the discretion of the Investigator.

- At Visit 5 used/unused study drug will be collected from subjects for drug accountability.
- Subjects will be instructed to use run-in (at Visit 1) or study drug on the day of visits (Visit 2, 3, 4, and 5) at least 2 hours prior to the start of the visit.
- Subjects will be instructed to immediately contact the site if there is any problem with the study drug (e.g. if the bottle was dropped or lost). In case the subject needs a replacement, the next bottle from the kit will be dispensed. If no bottle remains in the kit, a new kit will be assigned to the subject using the IWRS.
- 7.1.3 Instructions for Use and Administration

Subjects will be instructed to instill one drop in each lower eyelid two times daily (in the morning and in the evening before bed). Subjects will be instructed to use a second drop only if the first drop misses the eye. Subjects will receive detailed written instructions how to dose and complete their diary.

7.2 Other Study Supplies

Schirmer's test strips, sodium fluorescein, lissamine green, lissamine strips, Fluress, Tropicamide, InflammaDry.

8 STUDY METHODS AND PROCEDURES

8.1 Subject Entry Procedures

8.1.1 Overview

Subjects as defined by the criteria in sections 5.2, 5.3, and 5.4 will be considered for entry into this study.

8.1.2 Informed Consent

Before a subject's participation in the trial (i.e., changes in a subject's medical treatment and/or study-related procedures), the study will be discussed with each subject, and subjects wishing to participate must give written informed consent (and/or assent) using an informed consent form. The informed consent form must be the most recent version that has received approval/favorable review by a properly constituted Institutional Review Board (IRB).

8.1.3 Washout Intervals

Prohibiteed medications and treatments are listed in the Exclusion Criteria (Section 5.4) with their respective washout intervals.

8.1.4 Procedures for Final Study Entry

To qualify for Final Study Entry, each subject must meet all of the Inclusion Criteria (Section 5.3) and none of the Exclusion Criteria (Section 5.4).

8.1.5 Methods for Assignment to Treatment Groups:

Before the initiation of study run-in at Visit 0, each subject who provides written and informed consent will be assigned to a screening number. All screening numbers will be assigned in strict numerical sequence at a site and no numbers will be skipped or omitted. Each subject who meets all the inclusion and none of the exclusion criteria at Visit 0 and Visit 1 will be assigned a randomization number at the end of Visit 1. The IWRS will be used to assign all randomization numbers.

Randomization and kit numbers will be assigned automatically to each subject by strata as they are entered into the IWRS.

The site staff will dispense from this kit medication required until the next visit. Both the randomization number and the dispensed study drug kit number will be recorded on the subject's source document and electronic Case Report Form (eCRF). The rest of the kit will remain at the site and the site ensures that the same subject will receive study medication from the respective kit at his/her next visit. The sponsor, investigators, and study staff will be masked during the randomization process and throughout the study.

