10.3 Sample Size

One-hundred forty-two (142) ITT subjects (study eyes) per treatment group yields 90% power to reject H_{01} in favor of H_{A1} and conclude superiority of CyclASol over vehicle in the mean change from baseline corneal fluorescein staining (NEI scale) total score at Day 29 assuming a true difference (CyclASol minus vehicle) of -0.85, a common standard deviation of 2.2, and a two-sided alpha = 0.05. Additionally, 142 ITT subjects per treatment group yields 82% power to reject H_{02} in favor of H_{A2} and conclude superiority of CyclASol over vehicle in the mean change from baseline total OSDI score at Day 29 assuming a true difference (CyclASol minus vehicle) of -5.0, a common standard deviation of 14.5, and a two-sided alpha = 0.05. Accounting for subject discontinuations, 316 total subjects will be enrolled

For justification of clinical relevance of selected differences see Section 6.1.4.

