10.4.5 Primary Efficacy Analyses

The primary comparisons in this study will be between CyclASol versus vehicle at Day 29. The primary efficacy endpoints (e.g. change from baseline in corneal fluorescein staining [total NEI] and OSDI) will be analyzed separately using an ANCOVA model with terms for baseline value, treatment, and the interaction of treatment by baseline value (the interaction term will be maintained in the model only if the p-value for the term is <0.10).

Least squares mean for each treatment group and for the difference between treatment groups will be presented from the model together with two-sided p-values and 95% confidence intervals. In the event that the interaction of treatment by baseline value is significant, estimate and contrast statements will be used to determine the treatment group means and differences at the 25th, 50th, and 75th percentile of the baseline score over treatment groups.

Two-sample t-tests and Wilcoxon rank sum tests comparing treatment groups will be performed as sensitivity analyses. A mixed-effect repeated measures model will also be used as an additional sensitivity analysis of mean scores and mean changes from baseline at each visit. This model will include treatment, visit, and the interaction between treatment and visit as fixed effects, and subject as a random effect. An unstructured covariance matrix will initially be used to model the covariance among repeated measures; however, if the model fails to converge using this covariance structure, either heterogeneous TOEPLITZ, homogeneous TOEPLITZ, or CS (compound symmetry) will be implemented according to the Akaike information criterion with a correction for finite sample sizes (AICc). As an additional sensitivity analysis, a mixed-effect repeated measures model will be used with the covariance matrix selected from unstructured, heterogeneous TOEPLITZ, homogeneous TOEPLITZ and CS according to AICc.

10.4.8 Safety Variables

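### Randomization is stratified, but neither the primary ANCOVA nor the repeated-measures model includes the strata; if they predict outcome beyond baseline, the tests are conservative and some power is forgone

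*Combined protocol and SAP*

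**What the plan says.** Section 8.1.5 (Methods for Assignment to Treatment Groups) makes the allocation stratified: "Randomization and kit numbers will be assigned automatically to each subject by strata as they are entered into the IWRS". The visible text does not name the strata. The same section says "Both the randomization number and the dispensed study drug kit number will be recorded" for each subject.

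Section 10.4.5 says the two primary endpoints "will be analyzed separately using an ANCOVA model with terms for baseline value, treatment, and the interaction of treatment by baseline value", with the interaction kept only if its p-value is below 0.10. The synopsis gives the same model. For the repeated-measures sensitivity analysis, Section 10.4.5 says: "This model will include treatment, visit, and the interaction between treatment and visit as fixed effects, and subject as a random effect".

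No visible text puts a stratification factor in either model or explains its absence. The t-test and Wilcoxon sensitivity analyses are described only as comparisons of the treatment groups.

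**The concern.** Stratified allocation balances the arms within strata, so differences between strata contribute little to the sampling variation of the treatment contrast. If the analysis model omits the strata, that variation stays in the residual. The model-based standard error then overstates the true one, the test rejects too rarely under the null, and the confidence interval is too wide.

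This happens in the ANCOVA only if the strata predict the Day 29 change beyond the baseline covariate already in the model. The repeated-measures model lists no baseline term, so there the strata need only predict the outcome.

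What is at stake is precision. At equal explained variance the loss is larger for OSDI, which has the lower planned power and is tested only after staining succeeds. Which endpoint would actually be affected depends on the strata. A cut on baseline OSDI, for example, would leave the OSDI ANCOVA intact, and any loss would fall on staining.

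**Working it through.** **Inputs.** From Section 10.3: 142 per arm; staining difference -0.85 with "a common standard deviation of 2.2, and a two-sided alpha = 0.05"; OSDI difference -5.0 with "a common standard deviation of 14.5, and a two-sided alpha = 0.05". From Section 5.1: "at least 316 subjects at approximately 10 sites with 158 subjects per each of the two treatment arms". The documents give no figure for the share of variance that the strata explain after baseline (R²), so I assume 0, 5, 10 and 20%.

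**The plan's own figures.** With ncp = δ / (SD × √(2/142)):

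- Staining: 0.85 / (2.2 × 0.1187) = 3.256; power Φ(3.256 − 1.96) = 90.2% (noncentral t 90.1%). The plan states 90%.
- OSDI: 5.0 / (14.5 × 0.1187) = 2.906; power Φ(2.906 − 1.96) = 82.8% (noncentral t 82.5%). The plan states 82%.
- Enrolment: 142 / 0.90 = 157.8, so 158 per arm and 316 in total, as stated.

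**Effect of omitting the strata.** Let k = √(1 − R²), and assume ideal balance within strata. The true standard error is k times the one the model reports. Hence:

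- actual two-sided alpha = 2Φ(−1.96/k)
- excess CI width = 1/k − 1
- power without strata = Φ((ncp − 1.96)/k)
- power with strata = Φ(ncp/k − 1.96)

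Taking 2.2 and 14.5 as residual SDs after baseline:

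| R² | k | alpha without strata | CI too wide by | Staining, without vs with | OSDI, without vs with |
|---|---|---|---|---|---|
| 0 | 1.000 | 5.0% | 0% | 90.2 vs 90.2 | 82.8 vs 82.8 |
| 5% | 0.975 | 4.4% | 2.6% | 90.8 vs 91.6 | 83.4 vs 84.6 |
| 10% | 0.949 | 3.9% | 5.4% | 91.4 vs 92.9 | 84.1 vs 86.5 |
| 20% | 0.894 | 2.8% | 11.8% | 92.6 vs 95.4 | 85.5 vs 90.1 |

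Power forgone at R² = 5/10/20% is 0.8/1.5/2.7 points for staining and 1.2/2.4/4.6 for OSDI (differences taken before rounding).

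**If the SDs are raw-change SDs.** Suppose baseline explains a share b of the variance (also an assumption). Then ncp is divided by √(1 − b), there is more power in hand, and less is forgone:

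| b | ncp staining / OSDI | Staining points forgone, R² = 5/10/20% | OSDI points forgone, R² = 5/10/20% |
|---|---|---|---|
| 10% | 3.432 / 3.063 | 0.6 / 1.2 / 2.0 | 1.0 / 2.0 / 3.7 |
| 20% | 3.640 / 3.249 | 0.4 / 0.8 / 1.3 | 0.8 / 1.6 / 2.8 |
| 30% | 3.891 / 3.473 | 0.3 / 0.5 / 0.7 | 0.6 / 1.1 / 1.8 |

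The alpha and CI-width columns do not change with b.

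**Simulation checks** (284 subjects, blocks of 4 within strata, ANCOVA with baseline, 10,000 runs unless noted; the block size is an assumption):

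- Stratum is a median cut of the endpoint's own baseline, b = 0: OSDI power 82.7% without and 82.7% with strata; staining 89.8% and 89.9%. No loss.
- Binary stratum independent of baseline: null rejection without strata 4.6/3.9/2.9% at R² = 5/10/20%.
- Four strata, 8,000 runs: null rejection without strata 4.6/3.7/2.8%; with strata 4.9 to 5.3%.
- Ten sites as strata, where balance is less than ideal: null rejection without strata 4.9/3.9/3.2% (Monte Carlo error about 0.2). OSDI power with b = 0 is 83.1/83.6/85.4% without and 84.1/85.9/89.7% with strata.
- Model with no baseline term, own-baseline cut, baseline assumed to explain 20%: null rejection without strata 3.7%; OSDI power 83.3% without and 86.5% with strata. The no-loss case therefore does not carry over to a model that lacks baseline.

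**Price of the extra terms.** At R² = 0, nine added degrees of freedom (281 to 272) move the critical t from 1.9684 to 1.9687. Noncentral-t power goes from 90.05% to 90.04% (staining) and from 82.53% to 82.52% (OSDI). About twenty added degrees of freedom cost about 0.02 points.

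**The case against.** The strongest reply is that the harm depends on text we cannot see. The strata are not named, and Section 8.1.5 appears to have lost text around the sentence on strata. If the strata are cuts of the baseline scores, the matching ANCOVA loses nothing, and nothing visible makes a worse case more likely. Analysis text is missing too: the numbering runs from 10.4.5 to 10.4.8, and Section 10.5 has a heading but no content, so a stratum-adjusted supportive analysis may exist. R² and b are both assumed, and the largest figure (4.6 points) needs R² = 20% together with b = 0 and ideal balance. With ten sites at R² = 5%, the simulated null rejection of 4.9% shows no detectable conservatism. No promised power is missed: omitting useful strata still leaves power above plan.

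Most of this stands as a limit on size. The effect is conditional, the R² range is not evidence, and the loss is measured against a better model rather than against a protocol commitment. It does not remove the point. The primary-model sentence is intact in both the synopsis and Section 10.4.5, and it omits the factors used in allocation. An own-baseline cut protects only that endpoint's ANCOVA, not the other endpoint and not the repeated-measures model. If site is a stratum, neither model captures it. Not knowing the strata is a reason to make the instruction conditional, not to leave the model silent.

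**Conclusion.** The point holds as a worthwhile efficiency improvement. The plan allocates by strata and lists no stratification factor in the primary ANCOVA or the repeated-measures model. The treatment estimate is unbiased, type I error is not inflated, the fixed sequence remains valid, and the stated power is met.

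For the ANCOVA the loss ranges from nil (strata that are categories of the endpoint's own baseline) to 2.7 points for staining and 4.6 for OSDI at the top of the assumed range. At R² of 5 to 10%, with baseline explaining 20% of raw-change variance, it is 0.4 to 0.8 points for staining and 0.8 to 1.6 for OSDI. These figures rest on assumed R² and b and on near-ideal balance within strata. Confidence is medium, because the strata are not visible.

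**What to change.** In Section 10.4.5 and the synopsis, add the IWRS stratification factor or factors as fixed effects to the primary ANCOVA for both endpoints, and add them to the repeated-measures models. If site is a factor, or factors are crossed, prespecify a rule for pooling sparse strata before unmasking. A factor that is only a category of an endpoint's own baseline may be left out of that endpoint's ANCOVA, with the reason stated. That exception should not extend to a repeated-measures model without a baseline term.

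The cost is a short text change, plus the pooling rule where it applies. No new data are needed, because the IWRS assigns every randomization number and that number is recorded for each subject. The change should be made before unmasking, so that the choice of covariates cannot be read as data-driven.
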